10.3.4 Safety Variables

Safety assessments will include the evaluation of AEs, including local tolerability (stinging/burning, pruritus, and erythema), clinical laboratory assessments, vital signs, 12-lead ECGs, and physical examinations.

10.3.4.1 Clinical Laboratory Safety Assessments

10.3.4.1.1 Clinical Laboratory Tests to be Performed

Samples for the following laboratory tests will be collected at the time points specified in the Schedule of Events (Section 2.2).

Hematology:	hemoglobin, hematocrit, red blood cell (RBC) count, RBC indices, mean corpuscular hemoglobin, mean corpuscular hemoglobin concentration, platelet count (or estimate), white blood cell count including differential
Serum Chemistry:	albumin, total bilirubin, total protein, calcium, alkaline phosphatase, alanine aminotransferase, aspartate aminotransferase, blood urea nitrogen, creatinine, glucose, sodium, potassium, chloride, bicarbonate, lactate dehydrogenase, uric acid, total cholesterol, high-density lipoprotein, low-density lipoprotein, triglycerides
Coagulation Panel:	prothrombin time, partial thromboplastin time, fibrinogen
Urinalysis:	pH, specific gravity, blood, glucose, protein, ketones
Pregnancy Test:	for women of childbearing potential only; serum at Screening, urine at each other visit.
Serology	Hepatitis B surface antigen, and hepatitis C

All blood samples for the clinical laboratory tests must be taken in a fasting state, at least 8 hours after the previous drug application.

Blood and urine samples for hematology, and serum chemistry will be sent to a central laboratory for analysis. Urine pregnancy tests and dipstick will be conducted at the study sites.

10.3.4.1.2 Specimen Handling Requirements

The transmission of infectious agents may occur through contact with contaminated needles and blood or blood products. Consequently, appropriate blood and body fluid precautions should be employed by all study personnel involved in the collection of blood and handling of specimens in both the clinic and laboratory settings. Refer to current recommendations of the appropriate authorities.

In addition to appropriate handling of subject samples, specific regulations exist regarding the shipment of biologic/etiologic samples. Procedures and regulations for the packaging and shipping of infectious samples are outlined in the study laboratory manual. The investigator is responsible for ensuring that all study samples that are to be transported to another location are packed and shipped appropriately according to the applicable regulations.

Samples for assessment of clinical laboratory tests will be transported to the Clinical Reference Laboratory (see the study laboratory manual for addresses).

10.3.4.1.3 Evaluation of Clinical Laboratory Values

The normal ranges of values for the clinical laboratory assessments in this study will be provided by the responsible laboratory and submitted to Mayne Pharma LLC prior to beginning the study. They will be regarded as the reference ranges on which decisions will be made.

If a laboratory value is out of the reference range, it is not necessarily clinically significant. The investigator must evaluate the out-of-range values and record his or her assessment of the clinical significance in the appropriate eCRF.

All clinical laboratory values that in the investigator's opinion show clinically significant or pathological changes during or after termination of treatment must be reported as AEs and followed, as described in Section 11.2.5.

All measurements described in this section are recognized standard methods.

10.3.4.2 Clinical Examinations

10.3.4.2.1 Vital Signs

Vital signs, including height and weight (only assessed at Screening), blood pressure, and pulse will be measured.

10.3.4.2.2 Twelve-lead Electrocardiogram

A standard 12-lead ECG will be performed after the subject has been supine for at least 5 minutes. All ECG recordings will be identified with the subject number, date, and time of the recording. Gel ECG electrodes may be used for ECGs because they are more conductive and cause less trauma on compromised skin. Efficacy assessments should be conducted before ECGs to avoid possible artefact/changes from the ECG.

For subjects in the PK substudy, additional ECGs will be performed postdose during serial blood sampling on Day 1 and Day 30.

If there is a marked prolongation of the QT/QTc interval during treatment, a subject should be discontinued from the IP but remain in the study until full resolution of the event. The DSMB will be informed immediately of such an occurrence.

10.3.4.2.3 Physical Examination

A complete physical examination excluding the genitourinary examination will be performed at Screening, while limited physical examinations (to include head, eyes, ears, nose, and throat, cardiorespiratory, abdomen, and range of motion) will be performed as indicated in the Schedule of Events (Section 2.2).

10.3.4.2.4 Other Safety Variables

Local tolerability will be assessed on a 0-3 scale (none, mild, moderate, severe). All application site reactions will be recorded as TEAEs in the diary. These should include the date and severity of the TEAE.

10.3.4.3 Adverse Events

The definitions and management of AEs, and any special considerations for AEs, are provided in Section 11.

10.4. Procedural Adjustments Due to COVID-19

The coronavirus disease 2019 (COVID-19) global pandemic has impacted the free movement of the world's population, which has been restricted to control the spread of the disease. It is recommended that all sites and subjects comply with the applicable local and federal guidelines regarding the necessary and proper precautions regarding COVID-19.

Although it is preferable to conduct all necessary study assessments in person (onsite visits), this may not be possible as a result of COVID-19-related travel restrictions. To ensure the safety of subjects, investigators, and site staff, Visits 3-6 (Double-blind Period; [Table 2-1](#)), Visits 7-11 (OLE Period; [Table 2-2](#)) and unscheduled visits may be conducted remotely. Screening and baseline visits must be performed onsite only, and must be postponed or scheduled for when onsite visits can be safely conducted.

Procedural adjustments due to COVID-19 when it is inadvisable or not possible to conduct an onsite study visit are detailed in [Appendix B](#).

11. ADVERSE EVENTS

11.1. Definitions

11.1.1 Adverse Events

An AE is defined as any untoward medical occurrence in a patient or clinical investigation subject administered a pharmaceutical product that does not necessarily have a causal relationship with this treatment. An AE can therefore be any unfavorable and unintended sign (including an abnormal laboratory finding, for example), symptom, or disease temporally associated with the use of a medicinal product, whether or not related to the medicinal product.

Pre-existing diseases or conditions will not be considered AEs unless there is an increase in the frequency or severity, or a change in the quality, of the disease or condition. (Worsening of a pre-existing condition is considered an AE.)

Events that occur in subjects treated with control product are also considered AEs.

11.1.2 Adverse Drug Reaction

All noxious and unintended responses to an investigational product related to any dose should be considered adverse drug reactions (ADRs).

The phrase “responses to an investigational product” means that a causal relationship between an investigational product and an AE is at least a reasonable possibility, i.e., the relationship cannot be ruled out. All AEs judged by either the reporting investigator or the sponsor as having a reasonable causal relationship to an IP qualify as ADRs.

All AEs for which the judgment of relationship to IP is “possible” or higher will be considered ADRs. If a relationship to IP is not provided, then the AE must be treated as if it were “possible.”

11.1.3 Unexpected Adverse Event/Adverse Drug Reaction

An expected AE or ADR is one for which the nature or severity is consistent with the known AE profile of the product. For a preapproval test product, the known information is contained in the IB. For a marketed product, the known information is contained in the current package insert for the product.

An unexpected adverse event (UAE) or unexpected adverse drug reaction (UADR) is one for which the nature or severity of which is not consistent with the applicable product information (e.g., IB for an unapproved investigational product or package insert/summary of product characteristics for an approved product). For example, hepatic necrosis would be unexpected (greater severity) if the IB only listed elevated hepatic enzymes or hepatitis. Likewise, cerebral thromboembolism and cerebral vasculitis would be unexpected (greater specificity) if the IB only listed cerebral vascular accidents.

Furthermore, reports that add significant information on specificity or severity of a known, already documented adverse reaction constitute unexpected events.

11.1.4 Serious Adverse Events/Drug Reaction

A serious adverse event (SAE) is any untoward medical occurrence that at any dose:

- results in death
- is life-threatening
NOTE: The term “life-threatening” in the definition of “serious” refers to an event in which the subject was at risk of death at the time of the event; it does not refer to an event that hypothetically might have caused death if it were more severe.
- requires inpatient hospitalization or prolongation of existing hospitalization
NOTE: Inpatient hospitalization is defined as 24 hours in a hospital or an overnight stay. An elective hospital admission to treat a condition present before exposure to the IP, or a hospital admission for a diagnostic evaluation of an AE, does not qualify the condition or event as an SAE. Further, an overnight stay in the hospital that is only due to transportation, organization, or accommodation problems and without medical background does not need to be considered an SAE.
- results in persistent or significant disability/incapacity
- is a congenital anomaly
NOTE: A congenital anomaly in an infant born to a mother who was exposed to the IP during pregnancy is an SAE. However, a newly diagnosed pregnancy in a subject that has received an IP is not considered an SAE unless it is suspected that the IP(s) interacted with a contraceptive method and led to the pregnancy.
- is an important medical event
NOTE: Medical and scientific judgment should be exercised in deciding whether it is appropriate to consider other situations serious, such as important medical events that may not be immediately life-threatening or result in death or hospitalization but may jeopardize the subject or may require intervention to prevent one of the other outcomes listed in the definition above. Examples of such events are intensive treatment in an emergency room or at home for allergic bronchospasm, blood dyscrasias, or convulsions that do not result in hospitalization, development of drug dependency, or drug abuse. The occurrence of malignant tumors is also to be considered serious.

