11.2.2.2 Seriousness

The investigator is to evaluate whether the AE meets serious criteria, as described in Section 11.1.4.

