11.2.6 Reporting

11.2.6.1 Serious Adverse Events

The investigator or designee must report all SAEs promptly to Premier Research within 24 hours of first becoming aware of the event by e.g., completing, signing and dating the Serious Adverse Event Report Form, verifying the accuracy of the information recorded in the form with the source documents and eCRF, and sending the SAE form to the Premier Research by one of the following methods:

Email: [contact]

Email: [contact]

[contact]

[contact]

This written report should be submitted on the SAE form provided for this purpose. At the time of first notification, the investigator or designee should provide the following information, if available:

- Protocol number
- Reporter (study site and investigator)
- Suspect IP
- Subject's study number
- Subject's year of birth
- Subject's gender
- Date of first dose of IP(s)
- Date of last dose of IP(s), if applicable
- Adverse event term
- Date of occurrence of the event
- A brief description of the event, outcome to date, and any actions taken
- The seriousness criteria(on) that were met
- Concomitant medication at onset of the event
- Relevant medical history information
- Relevant laboratory test findings
- Investigator's opinion of the relationship to IP(s) ("Is there a reasonable possibility that the IP caused the SAE? Yes or No?")
- Whether and when the investigator was unblinded as to the subject's treatment assignment

Any missing or additional relevant follow-up information concerning the SAE should be sent to the sponsor/sponsor representative via the same contact details above as soon as possible on a follow-up SAE Report Form, together with the following minimal information (initial report, adverse event, date of occurrence, subject identification (ID), study ID, IP, and site number); this will allow the follow-up information to be linked to the initial SAE report.

Specific information may be requested by the Premier Research Pharmacovigilance Department using a follow-up request form or via email communication.

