13.1.6.2 Adverse Events

All AEs will be coded using the Medical Dictionary for Regulatory Activities (MedDRA), Version 20.1 or higher.

Treatment-emergent AEs are defined as:

- AEs with onset at the time of or following the start of treatment with IP through the Follow-up Visit or Early Termination Visit, whichever occurs first, or
- AEs starting prior to the start of treatment but increasing in severity or relationship at the time of, or following, the start of treatment with IP through the Follow-up Visit or Early Termination Visit, whichever occurs first.

The number and percentage of subjects with AEs will be displayed by each treatment group in the Double-blind Period and overall in the OLE by system organ class and preferred term. Summaries of AEs by severity and relationship to IP will also be provided. Serious adverse events and AEs resulting in discontinuation of IP will be summarized separately in a similar manner. Subject listings of AEs, SAEs, and AEs causing discontinuation of IP will be produced.

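### The note to the hospitalization criterion in Protocol 11.1.4 exempts every admission to evaluate an AE, so a new on-study event needing an inpatient work-up can be classed as nonserious

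*Protocol*

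**What the plan says.** Protocol Section 11.1.4 counts an event as serious if it "requires inpatient hospitalization or prolongation of existing hospitalization". The note below that criterion says "Inpatient hospitalization is defined as 24 hours in a hospital or an overnight stay" and puts no condition on why the subject was admitted. The note then names three exemptions:

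- elective admission for a condition that was there before exposure to the product;
- diagnostic admission: "a hospital admission for a diagnostic evaluation of an AE, does not qualify the condition or event as an SAE";
- an overnight stay "only due to transportation, organization, or accommodation problems and without medical background does not need to be considered an SAE".

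Section 11.2.2.2 sends the seriousness decision back to this definition: "The investigator is to evaluate whether the AE meets serious criteria, as described in Section 11.1.4".

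The label then decides the handling. Under Section 11.2.6.1 the investigator or designee "must report all SAEs promptly to Premier Research within 24 hours" of becoming aware of the event. Under Section 11.2.6.3 nonserious events are entered in the eCRF and passed by the CRO to the sponsor in monthly aggregate form. Section 13.1.6.2 adds: "Serious adverse events and AEs resulting in discontinuation of IP will be summarized separately". The other protocol version in the file, which enrols adults and adolescents, has the same wording in its Section 11.1.4.

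**The concern.** The purpose of the stay normally matters to seriousness only when the stay tells us nothing about a new event. That is the logic of the elective and non-medical exemptions. An admission to investigate an AE is different, because the AE is the reason for the stay. As written, the diagnostic exemption covers an event that began after the first application, that may be related to the product, and that was bad enough to keep the subject in hospital.

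Two things are at stake: how quickly such an event is reported, and whether SAE counts mean the same thing at each of the roughly 40 planned sites. The protocol does not say where diagnostic evaluation ends and inpatient care begins, so two investigators could classify the same admission differently and both follow the text.

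**Working it through.** No arithmetic applies. The check puts the sentences of Section 11.1.4 side by side and runs one test case through them.

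**The three exemptions compared**

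| Exemption | Limit in the text |
|---|---|
| Elective admission | Treatment of a condition that predates exposure |
| Non-medical stay | Logistics only, with no medical reason |
| Diagnostic admission for an AE | None on onset, severity, relatedness or length of stay |

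**Test case.** An AE starts after the first application. The subject is admitted and kept overnight so that the cause can be investigated. No other seriousness criterion is met.

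1. Hospitalization criterion: met, because the event led to an inpatient stay.
2. Definition of inpatient stay: met, because the subject stayed overnight.
3. Elective exemption: does not apply, because the condition is new.
4. Non-medical exemption: does not apply, because the stay has a medical reason.
5. Diagnostic exemption: applies. The event is nonserious.

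Without step 5 the event is an SAE. The diagnostic wording alone changes the result.

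**What follows from the label**

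| | SAE | Nonserious AE |
|---|---|---|
| Site to CRO | Within 24 hours (11.2.6.1) | eCRF entry, no 24-hour duty |
| CRO to sponsor | Not confined to the monthly aggregate | Monthly aggregate (11.2.6.3) |
| Separate SAE summary (13.1.6.2) | Included | Left out |
| General AE tables by severity and relationship (13.1.6.2) | Included | Included |

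The 24-hour duty and the monthly report are different links in the chain: the first runs from site to CRO, the second from CRO to sponsor. They should not be read as one clock.

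**The case against.** The best reply is that an explicit exception qualifies its rule. The criterion asks whether the event requires inpatient care, and an admission made only to investigate need not show that. The two accepted exemptions also cut into the 24-hour or overnight definition. This much stands: a reader might call the note a flat contradiction, but the text can be applied as written. The defect is an exemption too broad for the criterion it qualifies.

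It also stands that the exemption touches only the hospitalization criterion. An event that meets any other criterion is still serious, including the important-medical-event criterion: "Medical and scientific judgment should be exercised in deciding whether it is appropriate to consider other situations serious". That route depends on judgment, however, and so does not restore a uniform rule.

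Four stronger readings are tempting but not supported:

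- *The DSMB decision on Cohort B could turn on one mislabelled event, since 15 subjects at 1:1:1 is about 5 per arm.* Section 12 sets no SAE rate or threshold. The board sees unblinded aggregate safety and tolerability data, and Section 5.3 lets investigators and the medical monitor bring concerns to it.
- *Hospital observation of a QT change would go unnoticed.* Section 10.3.4.2.2 requires the DSMB to be told at once of marked QT/QTc prolongation, whatever the SAE label.
- *Such events are recorded for 14 days instead of 30.* The window in Section 11.2 concerns start dates after the last day of participation. The label matters there only for events starting more than 14 and up to 30 days afterwards, not for on-treatment events.
- *Many admissions would be affected.* The documents give no frequency of diagnostic admissions.

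**Conclusion.** The point holds as a drafting defect in the SAE definition. For a new on-study AE that needs an inpatient stay for work-up and meets no other seriousness criterion, the note removes the event from 24-hour reporting and from the SAE summary. The harm is later notice and SAE counts that may not be comparable across sites. The event is not lost from the data, because it stays in the eCRF and the general AE tables.

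The conclusion rests on two assumptions: that sites apply the note as written, and that the investigator does not class the event as an important medical event. The number of events affected cannot be estimated from the documents. The primary endpoint, the sample size and the DSMB procedure are not touched. The change is still worth making, because the study sets out to compare safety and the correction is small.

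**What to change.** In the note to the hospitalization criterion in Section 11.1.4, delete the words that exempt a diagnostic admission, so that the sentence covers only elective admission for a condition that predates exposure. If the sponsor wants to keep a diagnostic exemption, restrict it to conditions present before exposure to the product. Leave the elective and non-medical exemptions as they are. Make the same edit in any other protocol version still in force.

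Then check the recorded AEs with a hospital stay to see whether any was classed as nonserious on this ground, and reassess those found. The protocol gives no sign that such cases exist, so this is a check and not a presumption.

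The cost is one edited sentence in an amendment, a short note to sites, and possibly a few more SAE reports.

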11.1.5 Significant Adverse Events

Other significant AEs are defined as marked hematological and other laboratory abnormalities (other than those meeting the definition of serious) and any events that led to an intervention, including withdrawal of test drug, dose reduction, or significant additional concomitant therapy.

11.1.6 Treatment-Emergent Adverse Events

An AE is defined as treatment emergent if the first onset or worsening is after the first application of IP (trifarotene or vehicle) and not more than 14 days after the last application of IP.

11.2. Event Assessment and Follow-up of Adverse Events

The occurrence of an AE or SAE may come to the attention of study personnel during study visits and interviews of a study participant presenting for medical care or upon review by a study monitor.

All reported AEs, including local and systemic AEs not meeting the criteria for SAEs, will be captured on the appropriate eCRF. Information to be collected includes event description, time of onset, clinician's assessment of severity, relationship to study product (assessed only by those with the training and authority to make a diagnosis), and time of resolution/stabilization of the event. All reported AEs occurring while on study must be documented appropriately regardless of relationship. All reported AEs will be followed to adequate resolution.

Any medical condition that is present at the time that the participant is screened will be considered as baseline and not reported as an AE. However, if the study participant's condition deteriorates at any time during the study, it will be recorded as an AE.

Changes in the severity of a reported AE will be documented to allow an assessment of the duration of the event at each level of severity to be performed. AEs characterized as intermittent require documentation of onset and duration of each episode.

Study clinic personnel will record all reportable events with start dates occurring any time after informed consent is obtained until 14 (for nonserious AEs) or 30 days (for SAEs) after the last day of study participation. At each study visit, the investigator will inquire about the occurrence of AE/SAEs since the last visit. Events will be followed for outcome information until resolution or stabilization.

